5.2 Exclusion Criteria

Patients who meet any of the following criteria will be excluded from study entry:

- 1. Subject is known to be positive for HIV. (HIV testing is not required.)
- 2. Evidence of other clinically significant uncontrolled condition(s) including, but not limited to:
 - a. Uncontrolled and/or active systemic infection (viral, bacterial or fungal)
 - b. Chronic hepatitis B virus (HBV) or hepatitis C (HCV) requiring treatment. Note: subjects with serologic evidence of prior vaccination to HBV (i.e. hepatitis B surface (HBs) antigen negative-, anti-HBs antibody positive and anti-hepatitis B core (HBc) antibody negative) or positive anti-HBc antibody from intravenous immunoglobulins (IVIG) may participate.
- 3. Treatment with any of the following within 7 days prior to the first dose of venetoclax:
 - a. Steroid therapy for anti-neoplastic intent
 - b. moderate or strong cytochrome P450 3A (CYP3A) inhibitors (see Appendix C for examples)
 - c. moderate or strong CYP3A inducers (see Appendix C for examples)
- 4. Prior CLL therapy:
 - a. Biologic agent (monoclonal antibody) within 30 days for anti-neoplastic intent.
 - b. Chemotherapy (purine analog or alkylating agent) or target small molecule agent within 14 days or 5 half-lives (whichever is shorter), or has not recovered to less than CTC grade 2 clinically significant adverse effect(s)/toxicity(s) of previous therapy.
- 5. History of severe allergic or anaphylactic reactions to monoclonal antibody therapy
- 6. Known hypersensitivity to any of the study drugs
- 7. History of other malignancy that could affect compliance with the protocol or interpretation of results (example: patients with a history of curatively treated basal or squamous cell carcinoma of the skin or in situ carcinoma of the cervix are generally eligible. Patients with a malignancy that has been treated, but not with curative intent, will also be excluded, unless the malignancy has been in remission without treatment for 2 years prior to enrollment.)
- 8. Known active bacterial, viral, fungal, mycobacterial, or other infection (excluding fungal infections of nail beds); or any major episode of infection requiring treatment with IV antibiotics or hospitalization (related to the completion of the course of antibiotics) within 4 weeks before the start of Cycle 0
- 9. Major surgery (within 4 weeks prior to the start of Cycle 0), other than for diagnosis
- 10. Women who are pregnant or lactating
- 11. Uncontrolled diabetes mellitus (related to high dose steroid risk)

12. Myocardial infarction within 6 months of starting study drug or other clinically significant heart disease (NYHA class 3 heart failure, uncontrolled hypertension)

5.3 Prior and Concomitant Therapy

If a subject reports taking any over-the-counter or prescription medications, vitamins and/or herbal supplements or if administration of any medication becomes necessary beginning with the Screening visit through the end of the study, the name of the medication, dosage information including dose, route and frequency, date(s) of administration including start and end dates, and reason for use must be recorded on the appropriate case report form.

Subjects should receive full supportive care during study participation, including hematopoietic growth factors, transfusion of blood products, fluid and electrolyte replacement, and antibiotics when appropriate. Subjects who use oral contraceptives, hormone replacement therapy, or other maintenance therapy should continue their use.

Steroid therapy for anti-neoplastic intent is prescribed in Cycle 0. Aside from this, however, steroids for anti-neoplastic intent will not be allowed during or within 7 days of study treatment. Inhalational steroids for the treatment of asthma or COPD, topical steroids, replacement corticosteroid therapy for an inherited or acquired deficiency, or brief corticosteroids for rituximab infusion-reaction management or prevention are allowed.

In addition, limited corticosteroid treatment (i.e. for approximately 21 days with rapid taper) is allowed while on study for significant active autoimmune cytopenias, eg. Autoimmune hemolytic anemia (AIHA) or immune thrombocytopenia (ITP). IVIG (intravenous immune globulin) is also allowable. Eltrombopag is another treatment option for ITP.

Guidelines regarding excluded and cautionary medications are summarized in the following table.

Table 2: Excluded and Cautionary Medications (See Appendix C for Examples of the Medications)

Excluded

Anticancer therapies including chemotherapy, radiotherapy, or other investigational therapy, including targeted small molecule agents: Excluded 5 half-lives prior to first dose and throughout venetoclax administration (except the HDMP/R prescribed on study)

Biologic agents (e.g., monoclonal antibodies) for anti-neoplastic intent:

Excluded 30 days prior to first dose and throughout venetoclax administration (except the HDMP/R prescribed on study)

Excluded during ramp-up phase and Cautionary during maintenance/target dose:

Strong and Moderate CYP3A inhibitors

Exclude during ramp-up phase and consider alternative medications. If subject requires use of these medications at the cohort designated dose, use with caution and reduce the venetoclax dose by 50% for moderate inhibitors and at least 75% for strong inhibitors during co-administration. After discontinuation of CYP3A inhibitor, wait for 2 to 3 days before venetoclax dose is increased back to the initial maintenance/target dose.

Strong and Moderate CYP3A inducers

Exclude during ramp-up phase and consider alternative medications. If subject requires use of these medications at the cohort designated dose, use with caution and contact PI for guidance.

Cautionary (See Appendix C for examples)

Warfarin

P-gp substrates

BCRP substrates

OATP1B1/1B3 substrates

P-gp inhibitors

BCRP inhibitors

Furthermore, administration or consumption of any of the following starting 3 days prior to the first dose of venetoclax is restricted:

- a. grapefruit or grapefruit products
- b. Seville oranges (including marmalade containing Seville oranges)
- c. star fruit

Recommended concomitant therapies:

In addition to the cautionary/excluded medications, there are also recommended concomitant prophylactic therapies:

- Allopurinol (or alternative uric acid reducing drug, dosing per clinician judgement) is recommended starting 3 days prior to first treatment, until the completion of the venetoclax rampup (Cycle 1, Day 30)

- Acyclovir (or alternative anti-VZV / HSV drug, dosing per clinician judgement) is recommended for prophylaxis for patients in Arm 1, starting C0D1 to C2D28.
- Septra (or alternative anti-pneumocystis agent, dosing per clinician judgement) is recommended for prophylaxis for patients in Arm 1, starting C0D1 to C2D28.
- Fluconazole (or alternative anti-fungal agent, dosing per clinician judgement) is recommended for prophylaxis for patients in Arm 1, starting C0D1 to C0D21 (stopping 7 days prior to venetoclax).

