		- Patients will receive HDMP + Rituximab for 1 cycle, followed by reassessment of Tumor Burden, - Patients will initiate venetoclax dose ramp-up, with ramp-up schedule according to venetoclax package insert. Upon completion of ramp-up (venetoclax to 400 mg), all patients will continue Venetoclax 400 mg (or highest tolerated dose) for up to 2 years. Patients will also continue rituximab 500 mg/m2 q 28 days through Cycle 6. Endpoint Assessment: 1. Assessment of the disease burden after a maximum of 2 cycles of HDMP + Rituximab is the primary endpoint. 2. Assessment of the disease burden after 1 cycle of HDMP + Rituximab. 3. Clinical and laboratory TLS events between start of treatment and the completion of venetoclax dose-ramp up (Cycle 2, Day 1) 4. Presence or absence of detectable MRD in the marrow will be
		assessed after approximately 9 months of venetoclax and completion of treatment. 5. Radiology assessment after approximately 9 months of venetoclax and completion of study (unless prior imaging studies are without measurable disease)

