- Continue allopurinol, acyclovir, and septra (or equivalent drugs, unless contraindication). Must stop fluconazole 7 days prior to first venetoclax dose.
- Week 1: Venetoclax 20 mg daily
- Week 2: Venetoclax 50 mg daily
- Week 3: Venetoclax 100 mg daily
- Week 4: Venetoclax 200 mg daily
- Week 5: Venetoclax 400 mg daily
- TLS Monitoring per venetoclax package insert.

Cycles 2-6 (28 days in duration each): Venetoclax + Rituximab

- Continue Venetoclax 400 mg PO daily (or highest tolerated dose)
- Rituximab 500 mg/m2 on day 1 of each cycle.

Cycle 7-26: Single agent Venetoclax

- Continue Venetoclax 400 mg PO daily (or highest tolerated dose)

End of Study:

- Marrow biopsy and aspirate to assess for detectable CLL (MRD)

Long-term f/up: No specific visits required. With patient consent, date of progression or next CLL therapy will be recorded.

Concomitant Medications:

- It is prohibited to take other intended CLL therapies concurrently, including purine analog, alkylating drugs, other anti-CD20 monoclonal antibody, ibrutinib, Idelalisib, etc. Corticosteroids are permitted (in cycle 0 as CLL therapy; in cycles 2-6 as anti-CD20 infusion reaction prophylaxis; and at other times for treatment of conditions other than CLL).
- Required wash out for the above is 5 half-lives or 1 month, whichever is shorter.
- GCSF, EPO, and blood transfusion are not restricted, and can be used as clinically indicated or as per clinician judgement.
- TLS prophylaxis is recommended from 3 days prior to Cycle 0 Day 1 until Cycle 2 Day 1: Allopurinol 300 mg daily (dose modified if needed; alternative uric acid lowering medication can be substituted).
- Anti-Infection Prophylaxis is recommended from 3 days prior to Cycle 0 day 1:
- Fluconazole 100 mg daily (or alternative per clinician discretion) until Cycle 1 Day 21;
- Acyclovir 400 mg BID (or alternative per clinician discretion) until Cycle 3 Day 1 (or may continue longer)
- Septra DS BID 2 days/week (or alternative per clinician discretion) until Cycle 3 Day 1 (or may continue longer)

It is prohibited to receive live viral vaccines or other investigational agents.

Version: 5 (Dec-2024)

Subject Withdrawal or Treatment Discontinuation:

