6.3 Cycle 1: Venetoclax Ramp-up

Cycle 1 is 35 days in duration and consists of venetoclax dose-ramp up, following standard dosing and TLS risk mitigation strategies as per Venetoclax prescribing information.

On Day 1 of Cycle 1, the following are completed:

- History and physical examination including vital signs.
- Current medications will be recorded in the subject's medical record.
- Laboratory examinations: CBC w/differential, comprehensive metabolic panel, phosphorous, uric acid, LDH Collection of correlative research sample
- Dispense and take initial dose of Venetoclax 20 mg PO.
- Tumor lysis syndrome monitoring as per Appendix D and E, which includes additional chemistry monitoring, potential IV fluid administration, and potential inpatient hospitalization if clinically indicated and in accordance with venetoclax standard of care.

On Day 2 of Cycle 1, the following are completed:

- Laboratory examinations: hematology (CBC w/differential), comprehensive metabolic panel, phosphorous, uric acid, LDH.
- Dispensing Venetoclax 20 mg 6 day supply
- 2nd dose of venetoclax 20 mg PO after labs are resulted and reviewed by treating physician or investigator.
- Patients continue venetoclax 20 mg PO daily C1D2 C1D7.

On Day 8 of Cycle 1, the following are completed:

- Current medications will be recorded in the subject's medical record.
- Laboratory examinations: CBC w/differential, comprehensive metabolic panel, phosphorous, uric acid, LDH
- Dispense and take initial dose of Venetoclax 50 mg PO dose level.
- Tumor lysis syndrome monitoring as per Appendix D and E, which includes additional chemistry monitoring, potential IV fluid administration, and potential inpatient hospitalization if clinically indicated and in accordance with venetoclax standard of care.

On Day 9 of Cycle 1, the following are completed:

- Laboratory examinations: CBC w/differential, comprehensive metabolic panel, phosphorous, uric acid, LDH
- Dispensing Venetoclax 50 mg 6 day supply
- 2nd dose of venetoclax 50 mg PO after labs are resulted and reviewed by treating physician or investigator.
- Patients continue venetoclax 50 mg PO daily C1D9 C1D14.

On Day 15 of Cycle 1, the following are completed:

- Current medications will be recorded in the subject's medical record.
- Laboratory examinations: CBC w/differential, comprehensive metabolic panel, phosphorous, uric acid, LDH
- Dispense and take initial dose of Venetoclax 100 mg PO dose level. (7 day supply).

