- Tumor lysis syndrome monitoring as per Appendix D and E, which includes additional chemistry monitoring, potential IV fluid administration, and potential inpatient hospitalization if clinically indicated and in accordance with venetoclax standard of care.

(Only required if High Tumor Burden prior to venetoclax initiation): On Day 16 of Cycle 1, the following are completed:

- Laboratory examinations: CBC w/differential, comprehensive metabolic panel, phosphorous, uric acid, LDH
- 2nd dose of venetoclax 100 mg PO after labs are resulted and reviewed by treating physician or investigator.
- Patients continue venetoclax 100 mg PO daily C1D16 C1D21.

On Day 22 of Cycle 1, the following are completed:

- Current medications will be recorded in the subject's medical record.
- Laboratory examinations: CBC w/differential, comprehensive metabolic panel, phosphorous, uric acid, LDH
- Dispensing and initial dose of Venetoclax 200 mg PO dose level. (7 day supply).
- Tumor lysis syndrome monitoring as per Appendix D and E, which includes additional chemistry monitoring, potential IV fluid administration, and potential inpatient hospitalization if clinically indicated and in accordance with venetoclax standard of care.

(Only required is High Tumor Burden prior to venetoclax initiation): On Day 23 of Cycle 1, the following are completed:

- Laboratory examinations: CBC w/differential, comprehensive metabolic panel, phosphorous, uric acid, LDH
- 2nd dose of venetoclax 200 mg PO after labs are resulted and reviewed by treating physician or investigator.
- Patients continue venetoclax 200 mg PO daily C1D23 C1D28.

On Day 29 of Cycle 1, the following are completed:

- Current medications will be recorded in the subject's medical record.
- Laboratory examinations: CBC w/differential, comprehensive metabolic panel, phosphorous, uric acid, LDH
- Dispensing and initial dose of Venetoclax 400 mg PO dose level (7 day supply).
- Tumor lysis syndrome monitoring as per Appendix D and E, which includes additional chemistry monitoring, potential IV fluid administration, and potential inpatient hospitalization if clinically indicated and in accordance with venetoclax standard of care.

(Only required is High Tumor Burden prior to venetoclax initiation): On Day 30 of Cycle 1, the following are completed:

• Laboratory examinations: CBC w/differential, comprehensive metabolic panel,

phosphorous, uric acid, LDH

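### Section 5.3 dates the end of recommended allopurinol as Cycle 1 Day 30, one day after the first 400 mg dose, while the synopsis gives Cycle 2 Day 1; the Section 5.3 date should be aligned.

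*Combined protocol and SAP*

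**What the plan says.** The current text gives two end dates for recommended uric acid prophylaxis.

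- Section 5.3, under recommended concomitant therapies, runs allopurinol from 3 days before first treatment "until the completion of the venetoclax rampup (Cycle 1, Day 30").
- The synopsis, item 6.0, under concomitant medications, states: "TLS prophylaxis is recommended from 3 days prior to Cycle 0 Day 1 until Cycle 2 Day 1", and names allopurinol 300 mg daily.

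The end of the ramp-up is itself described in two ways.

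- For the tumor lysis syndrome (TLS) endpoint, synopsis item 4.0 and Section 4.2 both count events up to the "completion of venetoclax dose-ramp up (Cycle 2, Day 1").
- Synopsis item 4.0 and Section 4.1 also say: "Upon completion of ramp-up (venetoclax to 400 mg), all patients will continue Venetoclax 400 mg" (or the highest tolerated dose). This ties completion to reaching 400 mg.

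The schedule is clear. Section 6.3 states: "Cycle 1 is 35 days in duration and consists of venetoclax dose-ramp up". The synopsis lists "Week 5: Venetoclax 400 mg daily" as the last ramp-up step. The Day 29 entry in Section 6.3 reads: "Dispensing and initial dose of Venetoclax 400 mg PO dose level (7 day supply"). The synopsis entry for Cycle 1 also says: "Continue allopurinol, acyclovir, and septra (or equivalent drugs, unless contraindication").

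**The concern.** The two end dates are 6 days apart on the nominal schedule, and those days fall in the last ramp-up week, just after the final dose increase. Section 7.3.3 and Appendix D both describe the 5-week ramp-up as the period of TLS risk, with chemistry changes possible at each dose increase. Lowering TLS risk is the trial's rationale, and laboratory and clinical TLS through the end of the ramp-up are secondary endpoints.

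A prescriber working from Section 5.3 would find a specific day there and could stop allopurinol on it. Another working from the synopsis would continue for the rest of the week. Patients in one small trial could then have different stop dates for no clinical reason. Table 3 schedules no chemistry between Cycle 1 Day 30 and Cycle 2 Day 1. Under its note (d), the Day 30 visit is not required for patients with low tumor burden, or with medium burden and creatinine clearance of 80 mL/min or more. For those patients the last tabulated uric acid before Cycle 2 is on Day 29.

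**Working it through.** This is a day count. No sample size or power formula applies.

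**Inputs**

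- Five dose levels of 7 days each: synopsis item 6.0; Table 3, Cycle 1 note (a).
- Cycle 1 length of 35 days: Section 6.3.
- First 400 mg dose on Cycle 1 Day 29, with a 7-day supply: Section 6.3.
- End of allopurinol: Cycle 1 Day 30 (Section 5.3) or Cycle 2 Day 1 (synopsis item 6.0).
- Visit window for Cycle 1 of 0 or +14 days: Table 3, Cycle 1 note (a).

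**Reproducing the plan's own length.** 5 levels × 7 days = 35 days, as stated. The levels start on Days 1, 8, 15, 22 and 29. Week 5 at 400 mg is Days 29 to 35, which is 7 days. Cycle 2 Day 1 is nominally Day 36, so the two end dates differ by 36 − 30 = 6 days.

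**Week-5 days outside the recommendation, nominal schedule**

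| End date used | Covered | Not covered | Share of week 5 | Share of ramp-up |
|---|---|---|---|---|
| Day 30, counted as covered | Days 29–30 (2) | Days 31–35 (5) | 5/7 = 71% | 5/35 = 14% |
| Day 30, not counted | Day 29 (1) | Days 30–35 (6) | 6/7 = 86% | 6/35 = 17% |
| Cycle 2 Day 1 (nominal Day 36) | Days 29–35 (7) | none | 0/7 | 0/35 |

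**If the first 400 mg dose is k days late (k from 0 to 14).** It then falls on Day 29 + k, at the latest Day 43.

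- If Day 30 is a visit label that moves with Day 29, the count stays at 5 or 6 of 7 for every k.
- If Day 30 is a fixed day and counts as covered, the covered days are max(0, 2 − k). The uncovered days are 5 at k = 0, 6 at k = 1, and 7 of 7 from k = 2.
- If Day 30 is a fixed day and is not counted, the covered days are max(0, 1 − k). The uncovered days are 6 at k = 0 and 7 of 7 from k = 1.

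**Which date is out of line.** The words of Section 5.3 tie the end of allopurinol to completion of the ramp-up. Read with Section 4.2, which dates completion as Cycle 2 Day 1, those words agree with the synopsis. Only the date in parentheses conflicts.

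**The case against.** The strongest reply is that this is an editorial mismatch with a ready explanation. Day 30 is the last laboratory visit tabulated for Cycle 1, about 24 hours after the first 400 mg dose. In one of the plan's two senses, the ramp-up is complete once 400 mg is reached. Allopurinol is recommended and left to clinician judgement, and nothing in Section 5.3 forbids it after Day 30. The synopsis covers the whole week and continues allopurinol in Cycle 1. Section 6.1 has it prescribed with no stop date, and Appendix D lists it at every tumor burden level with no stop date. This is also a single-center study, so there is less scope for divergent practice.

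Most of that stands, and it is why the point is minor. It explains where the Day 30 date may have come from, but it does not reconcile that date with the synopsis.

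Two stronger readings are tempting, and the documents support neither.

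- A reader might infer that prophylaxis has to last 7 days after each escalation, because the Cairo-Bishop definition in Appendix B uses a 7-day window. That window says when laboratory abnormalities count as TLS and does not set a duration of prophylaxis. Appendix B also gives the Howard definition, which has no such window, and the venetoclax dose modification table refers to the Howard criteria. The support for covering week 5 is the 5-week risk phase in Section 7.3.3 and Appendix D.
- A reader might infer that the TLS rates will be higher or the endpoint compromised. The documents give no basis for an effect on the TLS rate, and the endpoint cut-off in Section 4.2 does not depend on the allopurinol date.

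**Conclusion.** The conflict is real and lies in current operative text: Section 5.3 and the synopsis give different stop dates for the same safety prophylaxis. On the nominal schedule, following Section 5.3 leaves 5 or 6 of the 7 days at 400 mg in week 5 outside its recommendation, against 0 of 7 under the synopsis. The range depends only on whether Day 30 itself is covered. It widens to 7 of 7 only if Day 30 is read as a fixed day and the first 400 mg dose slips past it.

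The 0 of 7 is also nominal. Table 3 allows Cycle 2 Day 1 to move by 14 days either way, so an early visit could fall within week 5.

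The consequence is minor. The count describes what one section recommends, not what patients will receive. The sample size, type I error, power and endpoint definitions are unaffected. The correction is still worth making, because a wrong stop date for a safety measure can be followed as written and the change has no drawback.

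**What to change.** In Section 5.3, replace the date in parentheses, Cycle 1, Day 30, with Cycle 2, Day 1. That matches the synopsis end date for allopurinol and the date of ramp-up completion in synopsis item 4.0 and Section 4.2. Nothing else is needed to resolve the conflict.

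If the sponsor also wants allopurinol to continue for at least 7 days after the first 400 mg dose when visits shift, that would be a new rule. It would have to go into both Section 5.3 and the synopsis; otherwise an early Cycle 2 Day 1 would again produce two different stop dates.

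The cost is one date in the protocol text, with no change to the analysis, the case report form or the sample size.

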6.0 Treatment Plan / Study Procedures

Table 3. Schedule of Events

		Cycle 0								
	Screen (within 30	_,								
Day(a)	day unless noted)	Day 1	day 2	day 3	day 4	day 22				
MD Visit	x	x	uu, z	udy 5	uuy 4	uuy 22				
Vitals signs	×	x	x	x	×	×				
vitais signs	•		_	 						
CBC diff	×	x	x	x	x	x				
CMP (b)	×	x	x	x	x	x				
Phos	_ ^	×	×	×	×	×				
Uric acid		х	x	x	х	×				
LDH		×	х	х	х	×				
Correlative Lab Draw		x		_ ^_	•					
CONTENTIVE LOS DIAW										
Hep B serologies	×									
The production of the producti										
Methylprednisolone		1000 mg/m2	1000 mg/m2	1000 mg/m2						
Rituximab		100 mg	375 mg/m2		375 mg/m 2					
Ritaxiiiiab		100 mg	373 mg/mz	373 mg/mz	373 mg/m2					
Ct or MRI thorax (c)	x					x{d}				
CT or MRI abdomen/pelvis (c)	×					x{d}				
Ci di wiki abdomeny pervis (c)	- ^					×(u)				
				 						
				1					 	
NOTES										
NOTES	() 5			0.1	a. L. (anh. 1.	avala narmitta	d if aubicat appallac	l ofter pretend	LuE approval)	
	(a) Protocol allowed									
	(b) CMP includes th bilirubin, alkaline pl		a, K, Chloride, I	oicarbonate, B	UN, creatinine,	giucose; calci	um; total protein, al	pum in, AST, A	LI, total	
	(c) MRI is allowed		lle control adio	atad						
	(d) Areas that did				1 F am in I	auta da ast o				
	(a) Areas that did i	iot nave enlarg	ea lymph noae	es greater than	1.5 cm in long	-axis do not re	equire re-im aging			
										I

	Cycle 1 (35 days)									
Day (a)	1	2	8	9	15	16 (d)	22	23 (d)	29	30 (d)
MD Visit	×		6	9	13	10 (u)	22	23 (u)	29	30 (u)
Vital signs	×									
vital signs										
CBC diff	×	×	×	×	×	x	×	x	×	x
CMP (b, c)	x (pre and 6-8 hr)	x{c}	x (pre and 6-8 hr)	x (c)	×	x	×	×	x	x
Phos (b)	x (pre and 6-8 hr)	x {c }	x (pre and 6-8 hr)	x {c }	x	x	×	x	x	x
Uric acid (b)	x (pre and 6-8 hr)	x (c)	x (pre and 6-8 hr)	x (c)	x	x (c)	x	x (c)	x	x{c)
LDH (b)	x (pre and 6-8 hr)	x {c }	x (pre and 6-8 hr)	x {c }	x	x (c)	x	x {c }	x	x{c)
Correlative Lab Draw	x									
Investigat Administration for TLC or extension in indicated (d)										
Inpatient Admission for TLS monitoring in indicated (d)	×	X	×	X						
				50 may	100 mg		200 mg		400 mg	
		20 mg x 6		50 mg x 6 day	x 7 day		x 7 day		x1wk	
Venetoclax (IDS) (e)	20 mg x 1	day supply		supply	supply		supply		supply	
		,								

NOTES

- (a) Protocol allowed date windows for Cycle 1 are 0 days or + 14 days. In other words, patients should take 7 days of each venetoclax dose level prior to dose escalation.
- (b) venetoclax dosing and lab monitoring is per label. Tumor lysis syndrome monitoring as per Appendix D and E, which includes additional chemistry monitoring, potential IV fluid administration, and potential inpatient hospitalization if clinically indicated and in accordance with venetoclax standard of care.
- (c) CMP includes the following: Na, K, Chloride, Bicarbonate, BUN, creatinine, glucose; calcium; total protein, albumin, AST, ALT, total bilirubin, alkaline phosphatase
- (d) For patients with high tumor burden OR median tumor burden AND creatinine clearance <80ml/min, TLS monitoring will be done according to US Prescribing Information, i.e. In hospital: For first dose of 20mg and 50 mg: Predose,4, 8, 12 and 24 hours; Outpatient: For subsequent ramp-up doses: Predose,6 to 8 hours, 24 hours. For patients with low tumor burden or medium tumor burden wuth creatinine clearance 80ml/min or greater, assessments will be done outpatient, and the day 16, 23, and 30 visits are not required.
- (e) Venetoclax is dispensed AFTER CBC diff, CMP, phos, uric acid, and LDH results are reviewed by PI, subI, or study team.

Cycle	Cycle 2	Cycle 3	Cycle 4	Cycle 5	Cycle 6
Day (a)	1	1	1	1	1
MD Visit	x	x	x	x	x
Vitals signs	х	x	x	х	х
CBC diff	x	х	x	x	x
CMP (b)	x	x	x	x	x
Phos	x	x	x	x	x
Uric acid	x	x	x	x	х
LDH					
Correlative Lab Draw					
D	500 / 0	500 / 0	500 / 0	500 / 0	F00 / 0
Rituximab	500 mg/m2	500 mg/m2	500 mg/m2	500 mg/m2	500 mg/m2
		400 v 1 ath	400 v 1	400 1	400 v 1
Vanataslay (IDS)	400 mg v 1 month sumply		400 mg x 1 month	400 mg x 1 month	400 mg x 1 month
Venetoclax (IDS)	400 mg x 1 month supply	supply	supply	supply	supply
	NOTES		 		
	(a) Protocol allowed date v	windows for Cycles 2	-22 are - 14 days or	+ 14 days	
	1` '		•	· ·	-1-:
	(b) CMP includes the follow			creatinine, giucose; c	calcium; total
I	protein, albumin, AST, ALT	, totai bilirubin, alkal	ine phosphatase		

Cycle	Cycle 7	Cycle 10	Cycle 13	Cyle 16	Cycle 19	Cycle 22	End of Study
Cyole	Cycle 7	Cycle 10	Cycle 15	Cylic 10	Cycle 13	Cycle 22	C24D28 +/- 14
Day (a)	1	1	1	1	1	1	days
MD Visit	x	×	×	×	x	x	x
Vitals signs	x	x	×	×	×	x	x
_							
CBC diff	x	x	×	x	×	x	x
CMP (b)	x	x	×	x	x	x	x
Phos	x	x	x	x	x	x	
Uric acid	x	x	x	x	x	x	
LDH							
Correlative Lab Draw							x
	400 mg x 3 month	-		400 mg x 3 month		-	
Venetoclax (IDS)	supply	supply	supply	supply	supply	supply	
Ct or MRI thorax (c)		x{d}					x (d)
CT or MRI abdomen/pelvis (c)		x{d}					x (d)
Marrow biopsy and aspirate procedure		x{e}					x {e }
Marrow flow cytometry		x{e}					x {e }
,		(- /					(- /
Hematopath review		x{e}					x{e}
•		. ,					. ,
		L					

